4.3. Summary of Relevant Clinical Studies

Previous studies in adults with DPT thermal burns have demonstrated that StrataGraft skin tissue is generally safe with salutary clinical outcomes in regard to closure of DPT burns and elimination of autograft placement in the majority of subjects.

The Phase 1b study, "Open-label, Controlled, Randomized, Multicenter, Dose Escalation Study Evaluating the Safety and Efficacy of StrataGraft® Skin Tissue in Promoting the Healing of the Deep Partial-Thickness Component of Complex Skin Defects as an Alternative to Autografting," (STRATA2011) was an open-label, dose-escalation, multicenter study evaluating the safety, tolerability, and efficacy of StrataGraft skin tissue in promoting the healing of complex skin defects containing intact dermal elements. In this study, StrataGraft skin tissue was applied once to DPT burns to assess autologous tissue regeneration with reduction or elimination of

Protocol MNK01053115

StrataGraft

Amendment 1

autografts. This study included subjects with thermal burns of 3 to 49% TBSA. Each subject had 2 comparable burn wound areas identified, excised to remove nonviable tissue, and randomized to receive StrataGraft skin tissue or autograft. Thirty subjects were enrolled with 10 subjects in Cohort 1 receiving up to 220 cm² of refrigerated StrataGraft skin tissue and 10 subjects in Cohort 2 receiving up to 440 cm² of refrigerated StrataGraft skin tissue. Ten subjects in Cohort 3 received up to 440 cm² of thawed cryopreserved StrataGraft skin tissue. None of the subjects treated with StrataGraft skin tissue exhibited any significant safety concerns and none underwent autografting prior to Day 28. Additionally, 27 of the 28 per-protocol subjects (96%) exhibited complete wound closure of StrataGraft treatment sites at Month 3. Molecular analysis of biopsies taken from treated wound sites at Month 3 demonstrated no evidence of StrataGraft skin tissue DNA, indicating that the cellular components of StrataGraft skin tissue were no longer present.

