3.7 Treatment and Exposure

The number of subjects with 1, 2, and 3 burn sites, and numbers of StrataGraft constructs applied (per site and total per subject) will be summarized.

The observation duration from Day 1 (application of StrataGraft) to end of study will be summarized.

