3.8.2 Other Endpoint Analyses

The other endpoints of this study are:

- **Proportion of subjects with confirmed complete wound closure of all treatment sites without autograft (i.e., complete re-epithelialization without drainage and subsequently verified with confirmation assessment) on or before Week 12, supported by photodocumentation.**

Complete wound closure is defined as 100% skin re-epithelialization in absence of drainage and without autograft placement. Successful wound closure in this study requires that complete wound closure on or before Week 12 is achieved without autograft placement and is confirmed at least 14 days following the initial observation of complete closure.

The investigator will evaluate the confirmation of complete wound closure either by direct clinician observation or by subject-provided photodocumentation.

The proportion of subject with all confirmed complete treatment site closure(s) including two-sided 95% confidence intervals based on the normal approximation to the binomial will be calculated and presented.

- **Proportion of subjects with confirmed complete wound closure of all treatment sites without autograft (verified with confirmation assessment) at each visit, supported by photodocumentation.**

The planned visits are Week 1, Week 2, Week 4, Week 8, Week 12, and Week 24. However, the subjects may show up at any visit, and number and percentage will be summarized. For each visit, the denominator of the proportion of subjects is based on the total number of subjects who provided data for the visit.

- **Proportion of subjects maintaining durable wound closure by Week 24.**

Durable wound closure by Week 24 is achieved when a subject with confirmed wound closure is observed as remaining closed at least 90 days after complete wound closure through Week 24. Two summaries will be performed: 1. Denominator is mITT population 2. The denominator will be based on subjects with confirmed wound closure of all treatment sites without autograft by Week 12. The number, percentage and two-sided 95% confidence intervals based on the normal approximation to the binomial will be calculated and presented.

- **Proportion of treatment sites with confirmed complete wound closure without autograft (i.e., complete re-epithelialization without drainage and subsequently verified with confirmation assessment) on or before Week 12 and supported by photodocumentation.**

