The treatment sites will be analyzed regardless of subject. Treatment site with confirmed wound closure requires treatment site complete closure on or before Week 12 is achieved without autograft placement and is confirmed at least 14 days following the initial observation of complete closure.

The investigator will evaluate the confirmation of complete treatment site closure either by direct clinician observation or by subject-provided photodocumentation.

The proportion of confirmed complete treatment site closure including two-sided 95% confidence intervals based on the normal approximation to the binomial will be calculated and presented.

- **Proportion of treatment sites maintaining durable wound closure by Week 24.**

The treatment sites will be analyzed regardless of subject.

Durable wound closure by Week 24 is achieved when a confirmed wound is observed as remaining closed at least 90 days after a confirmed complete wound closure through Week 24. Two summaries will be performed: 1. Denominator is all treatment sites 2. The denominator will be based on a confirmed treatment site wound closure by Week 12. The number, percentage and two-sided 95% confidence intervals based on the normal approximation to the binomial will be calculated and presented.

- **Time to first confirmed complete wound closure of all treatment sites in a subject without autograft (verified with confirmation assessment at least 14 days later).**

The event for Kaplan-Meier method will be the first occurrence of all confirmed complete wound closure without autograft in a subject (first observation of complete closure verified with a second observation of complete closure at least 14 days later). The time to first confirmed wound closure will be analyzed by the Kaplan-Meier estimation method. The period for this analysis is calculated as (the date of having the first confirmed event – the date of Day 1 + 1). Subjects not having any confirmed complete closure event during the study will have their time censored at the last available date in the study. Kaplan-Meier estimates by StrataGraft treatment area with confirmed wound closure will be presented for the following categories: $\leq 500 \text{ cm}^2$, $> 500 \text{ cm}^2$.

The Kaplan-Meier estimate will be computed to determine the median time to confirmed complete wound closure without autograft placement.

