3.8.3 Subgroup Analyses

The Proportion of subjects with confirmed complete wound closure without grafting on or before Week 12 and TEAE endpoints will be summarized by the following demographic and baseline characteristics:

- Race (white, non-white)
- Ethnicity (Hispanic, non-Hispanic)
- Age (<65, ≥ 65)
- Sex (Male, Female)
- StrataGraft treatment area ($\leq 500 \text{ cm}^2$, $> 500 \text{ cm}^2$)
- StrataGraft treatment area ($\leq 1000 \text{ cm}^2$, $> 1000 \text{ cm}^2$)
- Overall TBSA of wound burden defined as burns plus donor site area (< Median, \geq Median)
- Burn location (Anterior trunk, Anterior Upper Extremity (includes forearm + upper arm), Anterior Lower Leg, Anterior Thigh, Posterior Trunk, Posterior Upper Extremity (includes forearm + upper arm), Posterior Lower Leg, Posterior Thigh)

To further evaluate the burn location effect, Percent of Re-epithelialization without Grafting at each Visit, Proportion of subjects maintaining durable wound closure and POSAS by clinical visit in person by burn location will be summarized.

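### Subject-level closure requires every treated site to close, so the area subgroups and the area-split Kaplan-Meier cannot separate treated area from number of sites

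*SAP*

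**What the plan says.** SAP 3.8.2 defines the Week 12 closure endpoint per subject as "Proportion of subjects with confirmed complete wound closure of all treatment sites without autograft", and the calculation is "The proportion of subject with all confirmed complete treatment site closure(s) including two-sided 95% confidence intervals based on the normal approximation to the binomial". The time-to-closure analysis follows the same rule: "The event for Kaplan-Meier method will be the first occurrence of all confirmed complete wound closure without autograft in a subject". The slowest site therefore sets the subject's time.

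A subject may have one, two or three treated sites, with about 2000 cm² in total (Protocol 6.1; SAP 2.1). SAP 3.3 totals treated area per subject, with categories at 500 and 1000 cm². It also categorises the area of each individual site.

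Two displays then use treated area. SAP 3.8.3 states: "The Proportion of subjects with confirmed complete wound closure without grafting on or before Week 12 and TEAE endpoints will be summarized" by a list of factors that includes area at 500 and at 1000 cm². SAP 3.8.2 states: "Kaplan-Meier estimates by StrataGraft treatment area with confirmed wound closure will be presented for the following categories", namely up to 500 cm² and above it. Number of sites is in neither place, nor in the subgroup list of Protocol 13.3.4. It does appear in SAP 3.7, as exposure: "The number of subjects with 1, 2, and 3 burn sites, and numbers of StrataGraft constructs applied".

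SAP 3.8.2 also plans confirmed and durable closure per treatment site, pooled over subjects, and at-least-one-site summaries of initial closure. None of these is crossed with treated area or number of sites.

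**The concern.** Unless sites within a subject always agree, each added site lowers the chance that all close and lengthens the time until the last one does. Because area is summed over sites, subjects above an area cut-point plausibly have more sites. A lower or slower closure result in the larger-area group could then come from how the endpoint is built, with no difference in how a given area heals.

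The split matters in this study. The amendment history in the Protocol gives clinical study experience with larger treatment areas as a reason for doubling the area limit. Readers are therefore likely to look at the results by area, and as planned they cannot tell area from number of sites.

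**Working it through.** The documents state no figure for this effect, so there is nothing to reproduce. The size has to be computed from assumptions.

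**Inputs.** From the documents: 1 to 3 sites per subject, the all-sites rule, about 100 subjects, and one closure rate from the earlier Phase 1b study, 27/28 = 96.4% (Protocol 4.3), used here as a high per-site value. Assumed: per-site closure *p*, within-subject correlation ρ, and the mix of 1/2/3-site subjects in each area group.

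**Step 1: chance that all *k* sites close.** For independent sites this is p^k. For correlated sites (beta-binomial), with s = 1/ρ − 1 and a = p·s, it is the product of (a + j)/(s + j) over j = 0 to k − 1. For k = 2 this reduces to p² + ρp(1 − p).

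| p | ρ = 0 (k = 1/2/3) | ρ = 0.3 | ρ = 0.6 |
|---|---|---|---|
| 0.80 | 80/64/51% | 80/69/61% | 80/74/70% |
| 0.85 | 85/72/61% | 85/76/70% | 85/80/77% |
| 0.90 | 90/81/73% | 90/84/79% | 90/86/84% |
| 27/28 | 96/93/90% | 96/94/92% | 96/95/94% |

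As ρ approaches 1 the fall disappears.

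**Step 2: one worked gap with no area effect.** Assume 80/20/0% of subjects have 1/2/3 sites at or below 500 cm², and 30/40/30% above. With p = 0.85 and ρ = 0:

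- at or below 500 cm²: 0.8 × 0.850 + 0.2 × 0.7225 = 0.8245
- above 500 cm²: 0.3 × 0.850 + 0.4 × 0.7225 + 0.3 × 0.6141 = 0.7282
- gap: 9.6 points

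With ρ = 0.3 the gap is 6.3 points. For the same mix, p = 0.90 gives 6.9 and 4.5 points, and p = 27/28 gives 2.7 and 1.7 points (ρ = 0 and 0.3).

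**Step 3: range over other mixes.** Gaps for p from 0.80 to 27/28 and ρ from 0 to 0.6:

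| Imbalance | Sites 1/2/3, smaller vs larger area | Gap (points) |
|---|---|---|
| none | same in both groups | 0 |
| mild | 70/20/10 vs 50/30/20 | 0.4 to 4.5 |
| moderate | 70/25/5 vs 30/40/30 | 0.8 to 9.6 |
| strong | 90/10/0 vs 10/40/50 | 1.5 to 19.2 |

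With an assumed 50 subjects per area group, the 95% half-width of the difference is about 8 to 18 points.

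**Step 4: time to closure.** The median of the slowest of *k* lognormal site times was simulated (400,000 draws, no censoring), with an assumed per-site median of 28 days. It is 28/32/35 days for 1/2/3 sites at log-SD 0.4 and ρ = 0.6, and 28/41/50 days at log-SD 0.7 and ρ = 0. Under the moderate mix, the area-group medians differ by 31.7 − 29.4 = 2.3 days to 39.9 − 32.2 = 7.7 days, with no area effect.

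**Step 5: after the change.** If closure is compared within number of sites, the artefact is zero by construction when area has no effect. The cost is precision. With an assumed 50/33/17 subjects having 1/2/3 sites and independent sites, the 95% half-widths are 11.1/16.4/23.8 points at p = 0.80 and 8.3/13.4/21.1 points at p = 0.90.

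**The case against.** **Total area is a legitimate question.** Total treated area per subject is the quantity the protocol limits, and having more sites to heal is part of that burden. SAP 3.8 is purely descriptive and claims no causal effect of area. This stands, and it is why the total-area split should stay. It does not make the split interpretable as an effect of area alone.

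**The plan already has related summaries.** A reader might infer that number of sites is ignored altogether. The documents do not support that: SAP 3.7 tabulates it, and SAP 3.8.2 plans pooled site-level and at-least-one-site closure. The overall all-sites penalty will be visible. Only the cross with area or number of sites is missing.

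**SAP 3.8.3 does not state the all-sites rule.** It omits those words, and its burn-location row fits an all-sites endpoint poorly, since one subject can have sites in several locations. The rule is carried over from the SAP 3.8.2 definitions; for the Kaplan-Meier it is explicit. If an at-least-one-site rule were meant instead, closure would rise with number of sites and the area split would still be mixed.

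**The size rests on chosen inputs.** This stands. At 27/28 per-site closure, or with high correlation, the artefact is a few points at most in the mild and moderate cases and lies well inside the interval width.

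**The earlier study.** A reader might also infer that showing one-site subjects would make the result comparable with the 96% in Protocol 4.3. It would not. That figure is per-protocol, at Month 3, from areas of at most 220 or 440 cm². This study uses the mITT population, areas up to about 2000 cm², and confirmation at least 14 days later. No such comparison is planned.

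**Conclusion.** The point holds, limited to the descriptive comparison by area. The all-sites rule together with area summed over sites means that the 500 and 1000 cm² closure subgroups and the area-split Kaplan-Meier cannot separate treated area from number of sites.

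With no true area effect, the groups could differ by roughly 0 to 10 points under mild to moderate assumed imbalance, and by about 2 to 3 points at 27/28 per-site closure with the 80/20/0 versus 30/40/30 mix. The gap is zero if the mixes match or sites within a subject always agree. It would be larger only under a strong imbalance. Per-site closure, correlation and site mix are all assumptions; the documents give no data on site mix or correlation.

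Nothing here shows that an observed area difference would be an artefact. The plan as written simply could not tell. With no hypothesis tests, error rates are not at issue, and the primary TEAE endpoint is unaffected. This is a cheap improvement to interpretation.

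**What to change.** - Keep the total-area split in SAP 3.8.3 and in the Kaplan-Meier display, with a footnote that it is not adjusted for number of treated sites. State in SAP 3.8.3 whether closure there means all of the subject's sites.
- Add number of treated sites (1, 2, 3) as a factor for the Week 12 closure subgroup table and for the Kaplan-Meier display.
- Tabulate the planned site-level closure by each site's own area, using the per-site categories in SAP 3.3, with confidence intervals that allow for clustering of sites within subjects.

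The cost is SAP wording and a few more table rows and curves, from variables the SAP already plans to summarise. Three-site subjects are likely to be few, so their intervals will be wide and should be shown as such.

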3.8.4 Exploratory Analyses

Results from all Health Care Resource Utilization (HCRU) parameters as exploratory efficacy endpoints will be summarized with descriptive statistics. The exploratory endpoints are as following:

- Location of care for StrataGraft application (e.g. inpatient hospital, outpatient/ambulatory hospital, clinic, etc.)
- Treatments used for all other burn areas following excision and %TBSA treated with each (other than StrataGraft treatment sites)

- Number of Operation Room (OR) procedures required for burn treatment: excisions, application of StrataGraft and all other grafting procedures, including autografts, allografts, and xenografts
- Duration of OR procedure
- Length of hospital stay
- Prescription drugs given at discharge from the hospital for wound-related events including pain control, itch, psychotropics, and antibiotics
- Re-admission within 30 days after discharge
- Whether a re-admission is planned
- Length of hospital stay of re-admission

3.8.5 Multiplicity

Adjustment for multiplicity does not apply to analysis of the endpoints for this study.

3.9 Safety

3.9.1 Adverse Events

All adverse events (AEs) will be assessed and recorded before or after the first placement of study product. Adverse events will be coded using the Medical Dictionary for Regulatory Activities (MedDRA), version 23.0. Adverse event information includes system organ class, preferred term, severity, and seriousness, and the investigator's assessment of the relationship of the adverse event to the placement of study product.

The TEAE definition is described in section 3.8.1 .

The number of TEAE as well as the number and percentage of subjects who experienced at least one TEAE will be summarized for each system organ class and each preferred term. TEAE will also be summarized by maximum severity and by strongest relationship to SG treatment site for each system organ class and each preferred term.

The sites will be presented as SG treatment sites (A, B, C), pooled SG treatment sites, Non-SG Burn area, donor sites, and other. The pooled SG treatment site is counted if the event occurs for at least one of the treatment sites.

The following TEAEs will be summarized by frequency and percentage of subjects:

- All TEAEs by sites and overall
- TEAEs by maximum severity, site and overall

- TEAEs by relationship, site and overall
- TEAEs at SG treatment sites by relationship
- TEAEs at SG treatment sites by relationship and maximum severity
- TEAEs leading to withdrawal by sites and overall
- TEAEs leading to withdrawal at SG treatment site by relationship
- TEAEs of wound-infection by sites and overall
- Serious Treatment Emergent adverse events (TEAEs) by sites and overall
- Serious TEAEs at SG treatment sites by relationship

3.9.2 Laboratory Assessments

Hematology and biochemistry will be collected at baseline (Day 1 or possibly within 48 hours of surgery) and Week 12. Summaries of baseline assessment and change from baseline for laboratory assessments will be summarized by number of subjects, mean, standard deviation, median, minimum and maximum.

Hematology and biochemistry laboratory results will be classified as status of 'Low', 'Normal' and 'High' as defined by central lab', and in some cases, by the sites' laboratory normal range. Shift tables summarizing status of changes from baseline at Week 12 according to baseline status will be provided for subjects with both baseline and Week 12 results.

Hematology and biochemistry parameters will be categorized as normal, non-clinical significance and clinical significance at Baseline and Week 12 by the clinician according to the institutional SoC in the evaluation of study subjects. Shift tables of change from baseline to Week 12 will be created for laboratory results using clinically significant categories.

3.9.3 Vital Signs

Patients vital sign data was collected at each visit and visit for confirmation of healing. The average values and change from baseline in vital signs of body temperature, systolic blood pressure (SBP), diastolic blood pressure (DBP), HR, and respiratory rate, will be summarized for each visit.

3.9.4 Assessment of Tissue Architecture

A subset of 10 subjects (sourced from across all the sites) with closed wounds (from subjects who have achieved wound closure, across all the sites) will be separately consented to have a punch biopsy (measuring 3 mm) taken from the center of the healed burn wound, and another punch biopsy measuring 3 mm taken from non-burned healthy skin. A histological evaluation of both samples will be done to analyze and contrast the skin architecture in the healed burn wound with healthy skin. The biopsy will happen at the study visit Week 12, regardless of when wound closure occurs. The histological evaluation results will be summarized by healed burn wound and non-burned healthy skin.

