11. OTHER ASSESSMENTS

A subset of 10 subjects with closed wounds (from subjects who have achieved wound closure, across all the clinical sites) will be separately consented to have a punch biopsy (measuring 3 mm) taken from the center of the healed burn wound, and another punch biopsy measuring 3 mm taken from non-burned healthy skin. A histological evaluation of both samples will be done to analyze and contrast the skin architecture in the healed burn wound with healthy skin. The biopsy will occur at the study visit Week 12, regardless of when wound closure occurs.

Wound assessments will include measurements for average depth, length, and width for calculations of area and percent epithelialization. Wound assessments will be facilitated by photographs taken by the subject and/or taken by the clinical study site staff at study visits throughout the study.

Approved

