3 STATISTICAL METHODS AND CONVENTIONS

3.1 General Conventions

- Unless otherwise noted, the number of subjects (N), mean, standard deviation, median, minimum, and maximum will be presented for continuous variables and frequency and percentage of subjects in each category will be presented for discrete variables.
- Unless otherwise noted, confidence intervals (CIs) will be 2-sided 95% CIs.
- Listings will be sorted by subject identification, and date of the procedure or event.
- Statistical analyses will be done using Statistical Analysis Software (SAS[®]) version 9.4 or higher.
- The Kaplan-Meier estimate will be computed to determine the median time to first confirmed complete wound closure without autograft placement (date of closure is the date of the first observation of complete epithelialization without use of an autograft and confirmed with a second observation of complete closure at least 2 weeks after the first.). The 95% CI will be constructed with a generalized Brookmeyer and Crowley method.
- The Proportion and 95% CI of subjects will be calculated using the normal approximation to the binomial distribution.
- Listing will be provided for all related summary tables.

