3.8 Efficacy and Safety Analysis

There is no hypothesis testing for the study. All analyses are descriptive.

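### SAP 3.9.4 specifies only by-tissue summaries for biopsies that are paired within subject, and no within-subject contrast, although contrasting the two tissues is their stated purpose

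*SAP*

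**What the plan says.** SAP 3.9.4 defines the group as "A subset of 10 subjects (sourced from across all the sites) with closed wounds". Each of these subjects has one punch biopsy "taken from the center of the healed burn wound, and another punch biopsy measuring 3 mm taken from non-burned healthy skin". Both samples belong to one visit: "The biopsy will happen at the study visit Week 12, regardless of when wound closure occurs".

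The protocol gives the purpose in Section 11: "A histological evaluation of both samples will be done to analyze and contrast the skin architecture in the healed burn wound with healthy skin". The protocol synopsis and SAP 2.1 and 3.9.4 say the same.

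On analysis, SAP 3.9.4 has one sentence: "The histological evaluation results will be summarized by healed burn wound and non-burned healthy skin". Protocol Section 13 contains no histology analysis. The default in SAP 3.1 is that "mean, standard deviation, median, minimum, and maximum will be presented for continuous variables", with frequencies and percentages for discrete variables. Under SAP 3.1.1 all observed values are used and nothing is imputed. Neither document names a histological variable or scale, a paired statistic, or a rule for incomplete pairs.

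**The concern.** Each subject acts as his or her own control. The aim is "to analyze and contrast the skin architecture in the healed burn wound with healthy skin", which is a question about differences within a person. The specified summary treats the tissues as two groups and does not use the link between the samples.

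The natural questions are how far each subject's healed skin departs from that subject's own normal skin, how variable that departure is, and in how many subjects it occurs. The specified summary answers none of these directly. Protocol 4.2 counts the biopsy among the procedures beyond standard of care, with its own risks, and the healthy-skin sample is taken to serve this comparison.

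The SAP does specify within-subject summaries elsewhere. SAP 3.9.2 has change from baseline for laboratory values and shift tables restricted to subjects with both results, and SAP 3.9.3 has change from baseline for vital signs.

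**Working it through.** The documents give no sample size or precision figure for the biopsy subset, so there is no stated figure to reproduce. The check asks what two separate columns can and cannot determine. From the documents: 10 subjects, two samples each, two-sided 95% as the default confidence level (SAP 3.1). The data below are made up, and the correlations are assumptions.

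**1. Continuous or scored feature.** Let the healthy values be 1, 2, ..., 10 (mean 5.5, SD 3.03). Take two versions of the wound values.
- Version A: each wound value is the subject's own healthy value plus 2. The wound values are 3 to 12, with mean 7.5 and SD 3.03.
- Version B: the same ten wound values, assigned to subjects in reverse order. The mean is again 7.5 and the SD 3.03.

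The by-tissue tables are identical, and the mean difference is 7.5 - 5.5 = 2.0 in both. The within-subject differences are not alike:

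| | SD of differences | Range |
|---|---|---|
| Version A | 0 | 2 to 2 |
| Version B | 6.06 | -7 to 11 |

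**2. Binary feature.** Let h and w be the numbers of healthy and wound samples with the feature, and k the number of subjects with it in both. Then k runs from max(0, h + w - 10) to min(h, w). The discordant counts are h - k and w - k, and the number of subjects who agree is 10 - (h + w - 2k).
- h = 9, w = 6: k is 5 or 6. The discordant split is 4 vs 1 (5/10 agree) or 3 vs 0 (7/10 agree).
- h = 7, w = 5: k is 2 to 5. Agreement is 2, 4, 6 or 8 of 10.

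**3. One missing sample.** In version A, drop the wound sample of the subject with values 10 and 12. The wound mean becomes (75 - 12)/9 = 7.0 on 9 subjects, and the healthy mean stays 5.5 on 10. Subtracting the columns gives 1.5, although every complete pair differs by exactly 2.0.

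**4. Precision, for illustration only.** Assume equal SD in both tissues and within-subject correlation rho. Half-widths of a 95% interval for the mean difference, in SD units:
- Tissues treated as independent: t(18) × sqrt(2/10) = 2.101 × 0.447 = 0.94.
- Paired: t(9) × sqrt(2(1 - rho)/10), with t(9) = 2.262.

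| Assumed rho | sqrt(2(1 - rho)/10) | Paired half-width | Against 0.94 |
|---|---|---|---|
| 0 | 0.447 | 1.01 | about 8% wider |
| 0.3 | 0.374 | 0.85 | 10% narrower |
| 0.5 | 0.316 | 0.72 | 24% narrower |
| 0.7 | 0.245 | 0.55 | 41% narrower |

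The two are equal when 2.262 × sqrt(1 - rho) = 2.101, that is rho = 1 - (2.101/2.262)² = about 0.14. Below that value pairing gives no gain in width.

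**The case against.** The strongest reply is that a reader might infer that the contrast will never be made and the pairing is thrown away. The documents do not support that.
- The histological evaluation is itself meant to contrast the two samples and may do so qualitatively.
- SAP 5 and 6 place the programming specifications and table shells in separate documents, which were not available here.
- SAP 3.1 provides listings sorted by subject. With about 20 rows, a reader could match each wound to the same person's healthy skin.
- With complete pairs, the difference in means or proportions follows by subtracting the columns.

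All of this stands, so the claim is limited to what the SAP specifies. A listing is still not a summary, and subtraction gives neither the spread nor the discordant counts.

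A reader might also take the interval widths as a loss caused by the plan. They are not: no interval is planned for histology, equal SDs and the correlation are assumed, and the figures do not apply to a categorical readout. Nor can one claim that pairing removes body-site differences, because neither document says the healthy sample is matched to the wound's location.

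The study is descriptive ("There is no hypothesis testing for the study. All analyses are descriptive"), but so is the remedy. Missing samples are a possibility and are not predicted. Both biopsies belong to one visit, and reporting N for continuous summaries would usually reveal unequal columns.

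**Conclusion.** The point holds in this form: the samples are paired, the stated purpose is a contrast, and the SAP specifies only by-tissue summaries. These leave the spread of within-subject differences undetermined (SD 0 or 6.06 in the example) and likewise the number of discordant subjects (agreement from 2/10 to 8/10 in the example). This conclusion needs no assumption about correlation. Any gain in precision does, and it disappears below a correlation of about 0.14 under equal SDs.

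Severity is minor. The biopsies are an ancillary assessment in 10 subjects, absent from the primary, other and exploratory endpoints, and the primary safety result does not depend on them.

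**What to change.** In SAP 3.9.4, for subjects with both samples:
- for each continuous or scored feature, report the within-subject difference (wound minus healthy) with n, mean, SD, median and range, and optionally a descriptive paired 95% CI;
- for each categorical feature, give a wound-by-healthy cross-table with the discordant counts.

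Keep the by-tissue summary as supportive, and state how many subjects lack one of the two samples. The histological features and their scales have to be named, in the SAP or the programming specifications, before these tables can be programmed.

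The cost is a short addition to the SAP, the list of features, and one additional paired display. It needs no new data and no hypothesis test.
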